7.7.1 Derived and Transformed Data

Missing data on each variable will be recorded in the table and not considered in data analysis.

7.7.2 Statistical Methods

The statistical analyses described in this section will be performed as further outlined in the SAP, which will be finalized prior to database lock and will be included in the clinical study report for this protocol. The final SAP will take into account any amendment to the protocol.

General Statistical Methodology:

Descriptive statistics (mean, SD, median, interquartile range) will be provided for continuous variables according to the results of data normality tests. Frequencies and percentages will be presented for categorical and ordinal variables.

All analyzes will consider the security of the dataset.

Primary Outcome Analysis:

The primary outcome in this study is to look at the incidence of death in the treatment of patients who have kidney problems with CRRT or not.

Bivariate analysis was carried out using the chi square/fisher's exact test to see whether there was a difference in the incidence of death in treatment between groups (CRRT vs Non-CRRT)

which was then continued to the multivariate analysis stage if it had a p value <0.25 , multivariate analysis was carried out using regression multiple logistics with a significance level of 0.05 which shows that it is a variable that influences the incidence of death in care.

Secondary Endpoint Analysis:

The secondary outcome in this study is to look at the factors causing CRRT in patients undergoing cardiac surgery with AKI.

Bivariate analysis was carried out using the chi square/ Fisher's exact test to see whether there were differences in patient characteristics between patients who were given CRRT and those who were not, which was then continued to the multivariate analysis stage if it had a p value <0.25 . Multivariate analysis was carried out using multiple logistic regression with The significance level is 0.05 which shows that it is a variable that influences the incidence of CRRT use.

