6.1 Primary Objective

- To analyze the association between AKI with RRT and intra-hospital postoperative mortality in cardiac surgery patients compared with AKI patients without RRT

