6.2 Secondary Objectives

- To analyze the risk of intra-hospital post-surgical mortality in cardiac surgery patients who complicated with CSA AKI
- To compare the risk of intra-hospital post-surgical mortality in cardiac surgery patients who complicated with CSA AKI with requirement of RRT and without RRT
- To Identify and analyze perioperative factors that play an important role in the incidence of mortality in AKI patients after cardiac surgery

7 Research Methods

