7.3.1 Variables Operational Definition

Table 7.1 Dependent Variable

No.	Variable	Definition	Measured with	Scoring	Scale
1	In-hospital mortality	Patient dies in hospital during treatment after cardiac surgery (patient has never gone home or been discharged from hospital)	Medical record	0 = Not Died 1 = Died	Categorical

Table 7.2 Independent Variables

No.	Variable	Definition	Measured with	Scoring	Scale
1	Acute Kidney Injury	Patients with an increase in serum creatinine more than 1.5 times or > 0.3 mg/dL with urine output < 0.5 cc/kg/hour for 6 consecutive hours.	Medical record	0 = No AKI 1 = With AKI	Categorical
2	Renal Replacement Therapy	Use of a renal replacement therapy machine, either continuous (CVVH) or intermittent (HD), during the period the patient is treated post-operatively until discharge from the hospital.	Medical record	0=Not required 1=Required	Categorical
3	Age	calculated from the day of birth to the day the surgery was performed in years	Medical record	0 = ≤ 60 years 1 = > 60 years	Categorical

		These are surgical procedures undertaken by patients, divided into 5 categories:		
4	Type of valve surgery	1. Coronary Artery Bypass Graft (CABG) is a coronary heart bypass surgery	1 = CABG	
		2. Valves or heart valve surgery is surgery performed on heart valves	2 = Valves	
		3. Mixed valves are heart valve surgery performed simultaneously with other heart surgical procedures (for example coronary or vascular)	3=Mixed Valves	Categorical
		4. Congenital is surgery for congenital heart defects suffered by the patient	4= Congenital	
		5. Other is for surgery that is not included in the 4 categories above (for example Vascular)	5 = Others	
5	Diabetes Mellitus	Obtained from the history of the disease suffered and blood sugar laboratory results.	Medical record	0= No 1= Yes
6	Hypertension	Obtained from the history of the disease suffered by the patient/which was diagnosed	Medical record	0= No 1= Yes

		before undergoing surgery, where the increase in systolic blood pressure is above the normal limit, namely more than 140 mmHg and diastolic blood pressure is more than 90 mmHg.			
7	Serum Creatinine	Serum creatinine value > 3.0 obtained last before surgery, in mg/dL	Medical record	0= No 1= Yes	Categorical
8	History of Stroke	History of stroke diagnoses that the patient has experienced, either with or without sequelae	Medical record	0= No 1= Yes	Categorical

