7.7 Statistical Analysis Plan

All analyses will be performed on patients who underwent cardiac surgery in period between 1 January 2020 until 31 December 2022, with complication of acute kidney injury (AKI) postoperative. All data were retrieved from patient medical record retrospectively. There were no active observation or data retrieved directly from patients.

Data analysis will be carried out by the statistical team after the research samples have been taken and the data has been completed. The analysis was carried out using SPSS Version 29. and all statistical analysis plans have been completely documented in this statistical analysis plan.

Data that has been processed correctly is then analyzed by:

- a. Univariate analysis

This univariate analysis was carried out to obtain an overview of the frequency distribution of research subjects and the distribution of the proportion of cases and controls according to each independent variable (risk factor) studied.

- b. Bivariate analysis

Bivariate analysis was used to determine the relationship between the main risk factors and the incidence of death in hospital while also testing the research hypothesis using the chi square test.

c. Multivariate analysis

Multivariate analysis is carried out with the aim of describing the relationship between the dependent variable and the independent variable simultaneously in the population. Multivariate analysis was carried out by connecting several independent variables with one dependent variable simultaneously. Because the independent variables are categorical, logistic regression was used for the analysis.

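### The secondary analysis models CRRT use, which is the outcome of none of the four objectives, with no candidate list, no timing rule and a causal reading; CRRT also does not match the RRT definition in Table 7.2.

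*Combined protocol and SAP*

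**What the plan says.** Under its secondary endpoint heading, section 7.7.2 states: "The secondary outcome in this study is to look at the factors causing CRRT in patients undergoing cardiac surgery with AKI". The method is a chi-square or Fisher test of "differences in patient characteristics between patients who were given CRRT and those who were not". Variables with p below 0.25 go into a multiple logistic regression, and significance there at 0.05 is given a set interpretation: "which shows that it is a variable that influences the incidence of CRRT use".

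The objectives point elsewhere. The primary one (6.1) is "To analyze the association between AKI with RRT and intra-hospital postoperative mortality in cardiac surgery patients", with AKI patients without RRT as comparator. The three secondary ones (6.2) cover mortality risk in AKI patients, that risk with and without RRT, and "To Identify and analyze perioperative factors that play an important role in the incidence of mortality in AKI patients after cardiac surgery". Section 7.1 and Table 7.1 name one dependent variable, in-hospital death: "Patient dies in hospital during treatment after cardiac surgery". The bivariate analysis in section 7.7 likewise addresses "the relationship between the main risk factors and the incidence of death in hospital".

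Table 7.2 lists RRT among the independent variables and defines it as "Use of a renal replacement therapy machine, either continuous (CVVH) or intermittent (HD"), at any point from surgery to discharge.

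**The concern.** Three things do not fit together.

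- **Outcome.** The only analysis written under the secondary heading answers a question that no objective asks, and none of the three secondary objectives is specified there.
- **Interpretation.** The plan commits in advance to calling a significant variable an influence on CRRT use, but it neither names the candidates nor requires them to come before RRT. If postoperative items are admitted, a long ICU stay that resulted from RRT could appear in the final report as a factor behind RRT.
- **Exposure.** Section 7.7.2 speaks of CRRT where Table 7.2 defines RRT. This reaches the primary comparison as well, because section 7.7.2 labels its groups CRRT and non-CRRT there too.

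**Working it through.** The plan gives no sample size, event count or power for this model, so there is no figure to reproduce. The check is a comparison of sections and a count.

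**1. Objectives against outcome**

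| Place | Outcome | Role of RRT |
|---|---|---|
| 6.1 primary | in-hospital mortality | exposure |
| 6.2 first | in-hospital mortality | none |
| 6.2 second | in-hospital mortality | exposure |
| 6.2 third | mortality in AKI patients | not named; perioperative factors are the predictors |
| 7.1 and Table 7.1 | in-hospital mortality, sole dependent variable | independent variable |
| 7.7.2 secondary | CRRT use | outcome |

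Objectives with RRT or CRRT use as outcome: 0 of 1 + 3 = 4.

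**2. Possible candidates**

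- Table 7.2 has 15 variables. Removing AKI (an entry criterion) and RRT (the outcome of this model) leaves 15 − 2 = 13.
- Section 7.3 also collects sex, weight and height, which Table 7.2 omits: 13 + 3 = 16.
- Postoperative: items 11–15 (prolonged ventilation, prolonged ICU stay, IABP, inotropic and vasoactive drugs, furosemide infusion) = 5. Share: 5/16 = 31%.
- Intended as pre-surgery: items 3–10 (8) plus the 3 demographic items = 11. One caution: the diabetes definition draws on blood sugar results whose date is not given.
- If patient characteristics means baseline items only, the postoperative count is 0.

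**3. Timing**

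RRT counts at any time up to discharge. Section 7.3 lists no RRT start time, although the medical records named in section 7.4 may hold one. Ventilation beyond 48 hours and ICU stay beyond 5 days are settled only once those times have passed, so RRT may already have begun. None of items 11–15 is defined relative to RRT. Each could precede it or follow it.

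**4. CRRT against RRT**

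Under Table 7.2, a patient given only intermittent dialysis is scored as RRT required. Under section 7.7.2 read literally, the same patient falls in the non-CRRT group, in the primary and the secondary analysis alike.

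**5. Size of a pre-surgery model**

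Surgery type has five categories, so 4 parameters; the other seven of items 3–10 take 1 each: 4 + 7 = 11. Sex, weight and height, entered as single terms, add 3, giving 14. The Abstract puts RRT at 1–10% of AKI patients. At that background rate, each 100 AKI patients in the cohort would supply 1 to 10 RRT cases. Section 7.5 gives no number of patients, so the available RRT cases cannot be stated.

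**The case against.** The strongest reply has four parts.

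- **The objectives are not left without an analysis.** Sections 7.7 and 7.7.2 already give descriptive frequencies, chi-square or Fisher tests and multiple logistic regression for death, which largely serve section 6.2. This stands. A reader might infer that the secondary objectives go unanalysed, and the documents do not support that; the fault is that none is specified under the secondary heading.
- **Patient characteristics may mean baseline items.** This also stands as a possible reading. A reader might infer that the plan will report consequences of RRT as its causes. The documents show only that nothing prevents it.
- **Details may follow.** Section 7.7.2 refers to a SAP to be finalized before database lock, where a list could appear. Section 7.7, however, says the analysis plans are already fully documented in this plan. If finalization is still open, that is the moment to add the list.
- **Reach is limited.** Section 10.2 plans publication of the primary endpoint analysis. That lowers the stakes, but the final report in section 10.1 is to cover the study's results and their interpretation.

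**Conclusion.** The mismatch is certain: 0 of 4 objectives has RRT or CRRT use as outcome, and no other section supplies one. The missing candidate list, the missing timing rule and the causal reading of significance are equally plain on the text.

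The harm from timing is conditional. It requires that items 11–15 be candidates (5 of 16, 31%, on the broad reading; 0 on the baseline reading) and that RRT came before them in some patients. A reader might infer a bias in a particular direction; the documents contain no rates or timings from which to derive its size or direction.

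Nor does the timing point touch the unadjusted comparison of mortality by RRT. The adjusted one may be affected, since the same postoperative items can pass the p below 0.25 screen into the mortality model, again without a timing rule. The CRRT/RRT discrepancy is a separate matter and does reach the primary comparison, adjusted or not. How many patients had only intermittent dialysis is not stated.

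This should be corrected before analysis. It does not invalidate the study.

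**What to change.** 1. In section 7.7.2, make the secondary analysis match section 6.2: in-hospital mortality with 95% CI in AKI patients overall and by RRT, and the mortality-factor model for the third secondary objective. Report the RRT odds ratio in that model with and without Table 7.2 items 11–15, because these may precede or follow RRT.
2. Whether or not the RRT-predictor model is kept, reconcile CRRT in section 7.7.2 with RRT in Table 7.2, and use one definition in the primary and secondary analyses.
3. If the RRT-predictor model is kept, add a matching objective labelled exploratory. Limit candidates to items known before surgery: Table 7.2 items 3–10, with diabetes based on preoperative data, plus sex, weight and height. Leave out items 11–15. Limit the number of parameters to what the number of RRT cases can support. Replace *causing* and *influences* with *associated with*.

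The cost is SAP wording, a check that the diabetes entry rests on preoperative data, and a check that RRT is coded in line with the reconciled definition. No new data items are needed for the candidate list. The downside is that the RRT model would say nothing about postoperative events that came before RRT.

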7.7.3 Sequence of Analyses

Analysis was carried out after the research data was complete, in this study no interim analysis was carried out.

7.8 Limitations of the Research Methods

There are some limitations that should be considered in this study. First, due to the retrospective design used, there were some predictors of CSA-AKI that could not be included. Second, there were limitations in the capacity to do crosschecking due to inability to access patients directly, which may lead to confusion and heterogeneity of the dataset. Finally, data only included a single center, which may not reflect the actual demographics of patients and cardiac disease as distinguished from other centers.

However, the difference from real-life observational data, which is more essential to assess and improve clinical practice worldwide and complement randomized controlled trials by providing clinically relevant, real-world data and provide considerable health economic information.

7.9 Other Aspects

None

8 Protection of Human Subjects

8.1 Independent Ethics Committee or Institutional Review Board

Prior to commencement of the study at a given site, the protocol will be submitted together to the responsible IEC/IRB for its favorable opinion/approval. The written favorable opinion/approval of the IEC/IRB will be filed by the Investigator.

The IEC/IRB will be asked to provide documentation of the date of the meeting at which the favorable opinion/approval was given, and of the members and voting members present at the meeting. Written evidence of favorable opinion/approval that clearly identifies the study, the protocol version, and the subject information and consent form version reviewed should be provided.

8.2 Subject Information and Informed Consent

Since the data analysis was performed retrospectively derived from hospital electronic medical records (EMRs), the need for informed consent was waived.

Whenever important new information becomes available that may be relevant to the subject's consent, the written subject information sheet and any other written information provided to subjects will be revised by the Sponsor and be submitted again to the IEC/IRB for review and favorable opinion. The agreed, revised information will be forwarded to each subject in the study. The Investigator will explain the changes to the previous version.

8.3 Subject Identification and Privacy

A unique subject number will be assigned to each subject at inclusion. This number will serve as the subject's identifier in the study as well in the study database. The Investigator must ensure that the subjects' anonymity is maintained.

The Investigator should keep a separate log of subjects' identification numbers, names, addresses, telephone numbers and hospital numbers (if applicable). Only authorized persons will have access to identifiable personal details, if required for data verification. The Investigator is responsible for retrieving information from personal medical records. Data protection and privacy regulations will be observed in capturing, forwarding, processing, and storing subject data.

9 Management and Reporting of Adverse Events

This study design is retrospective study. All the events and incidences were already happened in the past period. This study does not interact directly to patients, there are no adverse events were caused directly by the study.

10 Plans for Disseminating and Communicating Study Results

After completion of the study, we shall prepare a final report of study results, in close collaboration with the coordinating Investigator. All publications and presentations should be based on the final study report.

10.1 Study Report(s)

The completed study will be summarized in a final report that accurately and completely presents the study objectives, methods, results, limitations of the study, and interpretation of the findings.

